8.2 Exclusion Criteria

Individuals meeting any of the following criteria at screening or baseline are ineligible to participate in this study:

1. Physician makes a decision that trial involvement is not in subjects' best interest, or any condition that does not allow the protocol to be followed safely
2. Known severe liver disease (e.g., Child Pugh score > 12, AST > 5 times upper limit)
3. Oxygen saturation (SaO₂)/SpO₂ ≤ 94% in room air condition, or the arterial oxygen partial pressure (PaO₂)/fractional inspired oxygen (FiO₂) ratio < 300 mmHg
4. Known allergic reaction to camostat mesilate or one of its excipients
5. Known severe renal impairment or receiving dialysis
6. Pregnant or breastfeeding, or positive pregnancy test in a pre-dose examination
7. Receipt of any experimental treatment for COVID-19, including agents with actual or possible direct acting antiviral activity, including, but not limited to, hydroxychloroquine, lopinavir/ritonavir, tocilizumab, ivermectin, or remdesivir within the 30 days prior to the time of the screening evaluation. No off-label use of a drug for COVID-19 is allowed.
8. History of human immunodeficiency virus infection on highly active antiretroviral therapy (HAART).

8.3 COVID-19 RT-PCR Test at Central Laboratory

Subjects who test positive for COVID-19 at the local laboratory will be enrolled if the subject meets all other entry criteria requirements. Nasal mid-turbinate swab samples are also to be obtained at the Screening/Baseline and Day 1 visit for central laboratory viral testing for COVID-19 as a baseline assessment and to test for viral shedding. If a subjects' test performed at the local laboratory is positive for COVID-19 but the test performed at the central laboratory is negative, the subject will stay in the study and complete all study visits. The reason for this is that RT-PCR testing is not sensitive enough to be accurate 100% of the time. These subjects will provide safety data for camostat mesilate. Statistical analysis for efficacy endpoints may be adjusted for subjects who fall into this category.

8.4 Rescreening

Individuals who sign the informed consent form (ICF) to participate in the study but who do not subsequently meet all the requirements as outlined in the inclusion and exclusion criteria and therefore do not enroll (screen failures) may not be rescreened.

8.5 Study Withdrawal, Removal, and Discontinuation of Subjects

Subjects who discontinue study treatment or who are withdrawn from the study for any reason must have the date and the reason for study discontinuation recorded on the electronic case

report form (eCRF). Subjects who discontinue early from the study will be asked to return to the study site within 3 to 7 days of the last administration of study drug to complete assessments as indicated in the Schedule of Assessments ([Table 1](#)) (Early Termination Visit).

In the event that a subject discontinues prematurely from the study because of a TEAE or SAE, the TEAE or SAE will be followed up until it resolves (returns to normal or baseline values) or stabilizes, or until it is judged by the investigator to no longer be clinically significant and thereafter until Day 28.

Upon discontinuation every effort will be made to follow the subjects until Day 28 for all study outcomes unless there is death of the subject, hospitalization, withdrawal of consent by the subject or the subject is lost to follow up.

Once a subject is withdrawn from the study, the subject may not reenter the study.

A subject may voluntarily withdraw or be withdrawn from the study at any time for reasons including, but not limited to, the following:

- AE and/or SAE
- subject withdrawal of consent: at any time, a subject's participation in the study may be terminated at his/her request or on the basis of the investigator's clinical judgment. The reason for subject withdrawal will be noted on the eCRF.
- intercurrent illness: a condition, injury, or disease unrelated to the primary diagnosis that became apparent during treatment and necessitated the subject's termination from the study
- general or specific changes in the subject's condition that renders him/her ineligible for further treatment according to the inclusion/exclusion criteria
- subject fails to adhere to the protocol requirements (e.g., drug noncompliance, failure to return for defined number of visits)
- lost to follow-up: the subject stopped coming for visits, and study personnel were unable to contact the subject
- pregnancy, as indicated in [Section 12.4.5](#).

Additionally, the Sponsor may stop the study at any time for safety, regulatory, legal, or other reasons aligned with good clinical practice (GCP). This study may be terminated at the discretion of the Sponsor or any regulatory agency. An investigator may elect to discontinue or stop the study at his or her study site for any reason, including safety or low enrollment.

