6.2.2 Secondary Endpoints

Survival/Mortality

- The overall survival rate (the proportion of randomized subjects who survive up to Day 15 and Day 28)

Clinical Improvement

- Time to resolution of fever from randomization up to Day 28
- Time to hospitalization or death following randomization up to Day 28
- Proportion of subjects with no viral shedding (yes/no) using RT-PCR at Day 7, Day 15, and at Early Termination (for subjects withdrawn prior to completing the 14-day treatment period)

Safety/Tolerability

- Incidence of AEs and SAEs of any grade from randomization up to Day 28
- Cumulative incidence of grade 3 and 4 AEs from randomization up to Day 28
- Incidence of discontinuation from study due to an AE/SAE (discontinued subjects will be followed up until Day 28)
- Change from baseline in clinical laboratory parameters
- Change from baseline in vital signs (heart rate, blood pressure, peripheral capillary oxygen saturation [SpO₂])

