7.1 Description of Overall Study Design and Plan

This is a randomized, double-blind, placebo-controlled study of camostat mesilate in ambulatory outpatients with confirmed COVID-19 with at least one risk factor for severe illness. Subjects will be randomized in a 2:1 ratio of camostat mesilate:placebo. Approximately 300 subjects are planned to be enrolled (200 subjects to camostat mesilate and 100 subjects to placebo). Subjects will be treated with camostat mesilate 200 mg orally QID for 14 days and receive local SOC in addition to study drug. Subjects in the control arm will receive 2 placebo tablets orally QID for 14 days, as well as local SOC. All subjects will be followed until Day 28. Subjects will complete a symptom eDiary daily from Day 1 (first dose of study drug) through Day 15. Subjects will be coming into the clinic for assessments on Day 1, Day 7 and Day 15. Mid-turbinate nasal samples will be obtained at Screening, Day 7 and Day 15. Instructions for obtaining proper nasal samples will be provided. Subjects who withdraw from the study prior to completion of the 14-day

treatment period will be asked to return for an Early Termination visit for blood draws and a mid-turbinate swab collection. On Day 28 (end of study), a study team member will record subject disposition.

Figure 1 presents the study design.

Figure 1. Study Schematic

Abbreviations: COVID-19 = coronavirus disease 2019; SOC=standard of care.

^a The Screening/Baseline and Day 1 visit assessments can be done on the same day.

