10.1 Study Visits

10.1.1 Screening/Baseline and Day 1 Visit

The following procedures and assessments will be done at the onsite Screening/Baseline and Day 1 visit:

- Verify subject has written notification from a local laboratory confirming COVID-19 infection within 72 hours of randomization (i.e., Day 1). In most instances, the Screening/Baseline visit will occur on the same date as Day 1. If needed, the Screening/Baseline may occur before Day 1 as long as randomization can be completed within the 72-hour window.
- Obtain informed consent
- Review of inclusion/exclusion criteria, including urine pregnancy test, if applicable
- Assign a subject ID number (ID number = XXX site number followed by 001, 002, 003 subject number)
- Obtain mid-turbinate nasal swab sample to be sent to the central laboratory to test for a baseline assessment and to test for viral shedding of COVID-19 by RT-PCR
- Draw blood for central laboratory testing
- Record demographics, medical history (including current COVID-19 symptoms), and concomitant medications
- Obtain vital signs (height, weight, heart rate, blood pressure, SpO2)
- Measure oral body temperature
- Perform randomization and dispensing of study drug
- Provide subject with instructions for accessing eDiary portal for collection of daily information
- Administer first dose of study drug after all assessments are completed
- Record of any TEAEs

10.1.2 Onsite Visits on Day 7, Day 15, Unscheduled Visit, Early Termination Visits / Telephone Visits on Day 21, Day 28

The following procedures and assessments will be done on Day 7, Day 15, Day 21, Day 28, and early termination by telephone or at onsite visits:

- Verify subject compliance for completing daily eDiary entries by accessing the web portal for the subject's eDiary
- Review concomitant medications and record any TEAEs
- Assess vital signs (heart rate, blood pressure, SpO2) during on-site visits only
- Measure oral body temperature
- Draw blood for central laboratory testing (Day 15, Unscheduled Visit and Early Termination) during on-site visits only

- Obtain mid-turbinate nasal swab sample for viral shedding test (Day 7, Day 15, and Early Termination Visits) for central laboratory during on-site visits only

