12.4 Adverse Events

12.4.1 Adverse Events

An AE is any symptom, physical sign, syndrome, or disease that either emerges during the study or, if present at screening, worsens during the study, regardless of the suspected cause of the event. All medical and psychiatric conditions (except those related to the indication under study) present at screening will be documented in the medical history eCRF. Changes in these conditions and new symptoms, physical signs, syndromes, or diseases should be noted on the AE eCRF during the rest of the study.

Subjects will be instructed to report AEs at each study visit. All AEs are to be followed up until resolution or a stable clinical endpoint is reached.

Each AE is to be documented on the eCRF with reference to date of onset, duration, frequency, severity, relationship to study drug, action taken with study drug, treatment of event, and outcome. Furthermore, each AE is to be classified as being serious or nonserious. Changes in AEs and resolution dates are to be documented on the eCRF.

For the purposes of this study, the period of observation for collection of AEs extends from the time the subject is administered study medication (Day 1) until Day 28 or early termination. Subjects with early termination will be followed up until Day 28. Follow-up of the AE, even after the date of therapy discontinuation, is required if the AE persists until the event resolves or stabilizes at a level acceptable to the investigator.

When changes in the intensity of an AE occur more frequently than once a day, the maximum intensity for the event should be noted. If the intensity category changes over a number of days, then those changes should be recorded separately (with distinct onset dates).

Specific guidelines for classifying AEs by intensity and relationship to study drug are given in [Table 3](#) and [Table 4](#).

Table 3. Classification of Adverse Events by Intensity

MILD: An event that is easily tolerated by the subject, causing minimal discomfort and not interfering with everyday activities.

MODERATE: An event that is sufficiently discomforting to interfere with normal everyday activities.

SEVERE: An event that prevents normal everyday activities.

Table 4. Classification of Adverse Events by Relationship to Study Drug

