2.3.3 Safety/Tolerability

- Incidence of AEs and SAEs of any grade from randomization up to Day 28.

- Cumulative incidence of grade 3 and 4 AEs from randomization up to Day 28.
- Incidence of discontinuation from study due to an AE/SAE (discontinued subjects will be followed up until Day 28).
- Change from baseline in clinical laboratory parameters (including platelet counts, liver function tests, and potassium levels, etc.).
- Change from baseline in vital signs (heart rate, blood pressure, peripheral capillary oxygen saturation [SpO₂]).

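### Protocol Section 8.5 makes hospitalization an exception to Day 28 outcome follow-up after discontinuation, so vital status for the survival endpoint may be missing in some discontinued, hospitalized subjects

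*Protocol*

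**What the plan says.** For subjects who have discontinued, Protocol Section 8.5 asks sites to keep following them to Day 28 "for all study outcomes unless there is death of the subject, hospitalization, withdrawal of consent by the subject"; loss to follow-up is the fourth exception. The paragraph just before it covers subjects who leave because of a TEAE or SAE. It has the event followed to resolution or stability and then on to Day 28, with no exception for hospitalization.

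Other sections set follow-up without that exception:

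- Protocol 7.1: "All subjects will be followed until Day 28", and at Day 28 "a study team member will record subject disposition".
- Protocol 6.2.2, within the endpoint on discontinuation for adverse events: "discontinued subjects will be followed up until Day 28". SAP 2.3.3 repeats this.
- Protocol 12.4.1, on adverse event collection: "Subjects with early termination will be followed up until Day 28".

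The endpoint that needs the data is in Protocol 6.2.2 and again in SAP 2.3.1: "The overall survival rate (the proportion of randomized subjects who survive up to Day 15 and Day 28". SAP 4.2.1 handles it in the same way as the primary outcome, which leads to the missing-data rules in SAP 4.1.7.

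**The concern.** Death ends follow-up. Withdrawal of consent and loss to follow-up can make it impossible. Hospitalization does neither: the site can still find out whether the subject is alive. Yet Section 8.5 puts it in the same list, and for all study outcomes, of which survival is one.

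The subjects concerned are known to have deteriorated. If their vital status is not sought, the gaps fall where deaths are most likely. At the planning event rates (30% placebo, 15% camostat) the gaps could also differ by arm. Survival to Day 15 and Day 28 would then rest partly on unknown outcomes in the subjects who matter most for it.

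**Working it through.** **1. The rules side by side, for a subject who has discontinued and is then hospitalized**

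| Place | Scope | Followed to Day 28? |
|---|---|---|
| Protocol 8.5, exception clause | all study outcomes | not required |
| Protocol 8.5, preceding paragraph | the TEAE/SAE that led to discontinuation | yes |
| Protocol 7.1 | all subjects, general | yes |
| Protocol 6.2.2 and SAP 2.3.3 | discontinuation due to AE/SAE | yes |
| Protocol 12.4.1 | AE collection after early termination | yes |

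The direct conflict is between 8.5 and 7.1. The other rows are narrower in scope, but they point the same way as 7.1.

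**2. What the planned analysis does with missing vital status**

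I read SAP 4.2.1 as carrying the rules of SAP 4.1.7 over to survival. There are then two branches.

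- *Multiple imputation.* The listed variables are age, BMI, sex, days since first symptom, and clinic temperature at Days 7 and 14. Hospitalization status is not listed, so the model does not use the fact that most clearly marks these subjects as high-risk.
- *Expected count below 5 in an arm.* Only the tipping-point analysis on exact tests is given.

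**3. Scale, under stated assumptions**

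From the documents: 100 placebo and 200 camostat subjects, with planning event rates of 30% and 15%. Subjects with a primary event: 100 × 0.30 = 30 and 200 × 0.15 = 30, or 60 in all. This is an upper limit on COVID-19 hospitalizations at those rates, because it includes ER-only visits and deaths.

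Assumed: a death risk *d* of 5%, 10% or 20% among these 60, and no other deaths. Total deaths are 60 × *d* = 3, 6 or 12. The only mortality figures in the protocol are 7.1% and 11.9% by 14 days (Section 5.1.1), from a remdesivir trial in hospitalized patients with severe disease. They lie within that range but describe a different population.

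Expected deaths on placebo from the pooled margins are one third of the total: 1, 2 or 4, all below 5. If expected counts are instead taken arm by arm from the planning rates, they are 30 × *d* = 1.5, 3 or 6 per arm, so the exact branch applies at 5% and 10% but not at 20%.

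Assumed: a share *f* of the 60, equal in both arms, has discontinued and has lost vital status. In the tipping-point grid the distance between best and worst case for the mortality difference is 30*f*/100 + 30*f*/200.

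| *f* | Unknown statuses (60 × *f*) | Best-to-worst width, percentage points |
|---|---|---|
| 10% | 6 | 3.0 + 1.5 = 4.5 |
| 25% | 15 | 7.5 + 3.75 = 11.25 |
| 50% | 30 | 15 + 7.5 = 22.5 |

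At *d* = 10% the assumed true mortality is 3/100 = 3.0% against 3/200 = 1.5%, a difference of 1.5 points, with 6 deaths in all. Already at *f* = 10% there are as many unknown statuses as deaths, and the grid spans 4.5 points. At *f* = 25% there are 15 unknowns against 6 deaths. The analysis shows the uncertainty but can say little about the effect.

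The documents do not give *f*. The SAP's allowance of about 7.5% (SAP 4.1.4) is for overall loss to follow-up and does not measure it.

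**The case against.** **The clause is narrow and other records remain.** It covers only subjects who have already discontinued, and Section 8.5 does not list hospitalization itself as a reason for withdrawal. Day 28 disposition is recorded (7.1) and the End of Study form records death (SAP 3.1). TEAE/SAE discontinuations and persisting adverse events are followed (8.5, 12.4.1), and SAP 4.3 records adverse events that lead to death as SAEs. This stands, and it is why vital status may be missed rather than will be. None of it overrides 8.5, though, and a form holds only what the site has sought. The expedited SAE route is also weaker than usual, because Protocol 12.4.2 does not treat death or inpatient hospitalization as an SAE in this study.

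**Section 7.1 is a summary and 8.5 the operative rule.** Fair, but that makes the literal reading of 8.5 more likely at a site. The clause was perhaps written with the primary composite in mind, where a hospitalization is already the event. Its words reach all outcomes.

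**Missing data are planned for.** True: SAP 4.1.7 provides imputation, completers, tipping-point and all-missing-as-failure analyses. They express the uncertainty; they do not restore the deaths.

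**A stronger reading to avoid.** A reader might infer that survival will be overstated and the treatment difference shrunk by a calculable amount. The documents do not support this. Such a figure needs an observed-cases analysis, which under SAP 4.1.7 is at most a sensitivity analysis, as well as loss shares that nobody has stated. Even then the direction is open. With *d* = 10% and observed mortality 30*d*(1 − *f*)/(N − 30*f*), the true difference of 1.50 points becomes:

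- 2.25/92.5 − 2.25/192.5 = 1.26 points with 25% loss in both arms;
- 2.7/97 − 2.25/192.5 = 1.61 points with 10% loss on placebo and 25% on camostat;
- 2.25/92.5 − 2.7/197 = 1.06 points with the two shares reversed.

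These shifts are small beside the standard error of about 1.9 points: √(0.03 × 0.97/100 + 0.015 × 0.985/200) = 0.019.

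**Conclusion.** The inconsistency is real and minor. As written, Section 8.5 permits a site to stop seeking vital status in a discontinued subject who is hospitalized, against Section 7.1 and to the possible cost of the Day 15 and Day 28 survival endpoint. Any resulting gaps would be related to the risk of death, and the planned methods would not fill them. How many subjects this concerns, and which way it would move the treatment difference, cannot be learned from the documents; the figures above are illustrations on assumed death risks and loss shares.

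Two wider inferences do not hold. Hospitalized subjects in general are not dropped from follow-up, because the clause reaches only those who have discontinued. The primary endpoint is essentially unaffected: a COVID-19 hospitalization or ER visit is already an event, and SAP 3.1 counts any hospitalization or ER visit on the End of Study form as one.

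**What to change.** Reconcile Section 8.5 with Sections 7.1, 6.2.2 and 12.4.1 and with SAP 2.3.3, so that hospitalization is no longer an exception to ascertaining vital status. Add to 8.5 that vital status at Day 15 and Day 28, with the date of any death, is sought for every randomized subject who has not withdrawn consent, including discontinued subjects who are in hospital.

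The means already exist: the "Telephone Visits on Day 21, Day 28" named in the heading of Section 10.1.2, and the End of Study form. Where a subject cannot be reached by telephone, the site can ask the hospital or family. A date of death obtained at either call settles both time points.

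Striking the word from the list outright would go too far, since it would extend the follow-up duty to swabs and temperatures in inpatients. Only vital status is at issue, and other outcomes need not be pursued there.

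The cost is a short protocol amendment submitted to the IRB (Section 14.7.1) and minor site effort. The sample size does not change.

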9 TREATMENTS

9.1 Details of Study Treatments

Camostat mesilate, N, N-dimethylcarbamoymethyl 4-(4-guanidinobenzoyloxy)-phenylacetate methanesulfonate, a guanidinobenzoic acid derivative is an orally active protease inhibitor with potent inhibitory effects on trypsin, plasma kallikrein, plasmin, thrombin, C_{1r} and C₁ esterase but does not attenuate α -chymotrypsin, pepsin, or pancreatin. Camostat mesilate is presented as a film-coated tablet that is white to yellowish white in appearance. Each tablet contains 100 mg camostat mesilate.

All drug supplies will be provided by the Sponsor. Camostat mesilate will be manufactured in tablet form by Nichi-Iko Pharmaceutical Co., Ltd. (Japan). Placebo tablets will be manufactured by Stason Pharmaceuticals, Inc. (Irvine CA).

Active Treatment Arm: two 100 mg tablets of camostat mesilate taken orally QID (total daily dose of 800 mg)

Placebo Arm: 2 matching placebo tablets taken orally QID

Study drug will be supplied in high density polyethylene (HDPE) bottles, each bottle containing 112 tablets of active drug or matching placebo. Each bottle will be labeled with a randomized bottle number, the name and address of the Sponsor, expiration date, and other information required by the US Food and Drug Administration (FDA) regulations.

Study drug must be stored at controlled room temperature (15°C to 30°C; 59°F to 86°F) in a limited access, secured storage area until dispensed. The storage conditions should be monitored daily.

9.2 Dosage Schedule

Study drug is administered as 2 tablets taken orally QID for 14 days. Study drug should ideally be taken with a meal or snack (breakfast, lunch, dinner), but it is not required. Tablets should be taken 3 times during the day and the fourth dose should be taken in the late evening (bedtime), with the dosing spaced approximately 5 hours apart. If a subject misses a dose, there should be no less than 2 hours between doses.

9.3 Measures to Minimize Bias: Study Treatment Assignment and Blinding

9.3.1 Method of Study Treatment Assignment

Subjects will be screened and enrolled in the order they present to the study centers and will be assigned the next available sequential subject number.

According to the randomization schedule as indicated in the Schedule of Assessments ([Table 1](#)), the investigator or designee will obtain the randomization number from the IWRS software. The IWRS software will use the blinded study arm linked to the randomization number to select a bottle number containing the correct study product (active or placebo) which is known to the IWRS to be in the possession of the site. The pharmacist or designee will provide the assigned bottle to the subject. No

study site personnel, subjects, Sponsor personnel, or Sponsor designees will be unblinded to treatment assignment throughout the duration of the study unless unblinding is required. If an investigator becomes unblinded to a given subject's study treatment, that subject will be discontinued from the study unless there are ethical reasons for that subject not to be discontinued; approval from the Sponsor's Medical Monitor must be obtained in such instances.

In the event that emergency unblinding is required for a given subject because of AEs or concerns for the subject's safety or wellbeing, the IWRS software will perform the unblinding. The IWRS software limits access to the emergency unblinding function to designated personnel and records the date, time, and person performing the unblinding. The unblinding and its cause will also be documented on the eCRF via automated entry by the IWRS.

